5.7 Summaries of Intragastric pH-metry

The Full Analysis Set for pH measurements is defined in the SAP addendum. pH measurements will be analyzed as per SAP addendum Full Analysis Set #2 "Statistical analysis of either channel 1 or 2 depending on which is deemed to be showing intragastric pH. Exclusion of "air measurements" is applied."

Exploratory analyses will be performed based on Full Analysis Sets #1 and #3 in the SAP addendum.

Descriptive statistics of HTR pH >4, pH >5, and pH >6 over a 24-hour period during baseline, day 1, day 14 and day 15, will be presented by dose group.

A Mixed Model for Repeated Measurements (MMRM) will be utilized to analyze the percentage of time with intragastric pH >4, pH >5, and pH >6 (each pH cut-off separately), from now on referred to as Holding Time Ratio (HTR). The model will include the dose group, day (day 1, day 14) and the interaction between the dose group and day as fixed effects, the corresponding baseline HTR as a covariate and subject as a random effect. Least Squares Means (LSMs), together with their corresponding 95% confidence intervals (CI) will be used to estimate the HTR for each dose group and day.

The LSMs of HTR pH >4, pH >5, and pH >6 will also be graphically displayed together with their corresponding 95% CIs by visit (day 1 and day 14) for each dose group. As a sensitivity analysis a MMRM-model (separately for the three pH cutoffs) excluding the baseline covariate will also be fitted to support the results from the primary statistical model.

The trajectories (profiles) for the average 24-hour intragastric pH (pH values averaged over subjects for each 10-minute median value) will be plotted for day 1 and day 14 separately. The plot for each day will show the mean 24-hour intragastric pH for the six dose groups and baseline.

Bar plots for the frequencies of subjects showing the HTR (0-60, 60-80, 80-85, 85-90, 90-95, 95-100) with gastric pH >4, pH >5, and pH >6 over a 24-hour period during baseline, day 1, day 14 and day 15, will be presented by dose group. The horizontal axis of the bar plot will represent categorized HTR with gastric pH >4, pH >5 or pH >6 over a 24-hour period.

Descriptive statistics will be presented for the mean intragastric pH 0-12 hours and 12-24 hours and 0-24 hours after dose (mean within individuals over 0-12 hours, 12-24 hours and 0-24 hours after dose morning dose for BID, evening dose for QD) for days 1 and 14 by dose group.

The mean intragastric pH 0-12 hours, 12-24 hours and 0-24 hours after dose (morning dose for BID, evening dose for QD) for day 1 and 14 will be plotted together and separately, with their corresponding 95% confidence intervals in a graph displaying the mean values by visit for each dose group.

5.7.1 Relationship between plasma concentration of Linaprazan and intra gastric acid secretion (pH)

To illustrate the association between pH and the linaprazan concentration, scatterplots with pH on the y-axis and a horizontal line to illustrate pH >4, and linaprazan concentration in the x-axis will be plotted. These scatterplots will be presented as follows: i) QD dosing groups, ii) BID dosing groups, iii) all dosing groups. All dosing groups in one scatterplot will be presented for Day 1, Day 14 and together. All measurements from within <2h after first dose on Day 1 will be omitted from the scatter plots.

Line plots with two y-axes (primary y-axis: pH, and secondary y-axis: plasma concentration of linaprazan) against time will be presented for the average pH and average concentration data added with error bars for the standard errors of the means. Three separate plots will be generated, i) QD dosing groups, ii) BID dosing groups, iii) all dosing groups. In the plots both the means pooled over the mentioned dosing groups and the mean for individual dosing groups will be presented for Day 1, Day 14 and together.

Also, scatterplots relating HTR for pH >4 and pH >5 versus linaprazan exposure parameters (AUC, Cmax and Cmin) (ref: Scarpignato et al 2023) will be produced, to explore which PK-parameter would be most relevant. The HTR response within each subject will be explored as well. Three separate plots will be generated, i) QD dosing groups, ii) BID dosing groups, iii) all dosing groups. All plots will be presented for Day 1, Day 14 and together. All measurements from within <2h after first dose on Day 1 will be omitted from the scatter plots.

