3.3 Randomization and Blinding

Block randomization (block size=6) stratified by gender will be used to generate the randomization list, which will show the assignment of subjects to 1 of the 6 dose groups given in Section 3.1.

The randomization list of the study was be prepared by a statistician at CRS [name], and transferred to the Trial Master File (TMF) for archiving.

As this is an open label study, the dose group to which each subject is allocated will be recorded in the eCRF. A computer-generated randomization list will be created using SAS Proc Plan, SAS Version 9.4 or later (SAS Institute, Inc., Cary, NC) or equivalent program. The randomization list will contain subject number, block, gender, drug holiday period, and dose group.

The randomization list will be generated and kept by CRS.

No blinding procedures will be followed.

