3.4 Number of Subjects

3.4.1 Sample Size

Approximately, 116 healthy volunteers are planned to be screened to achieve 72 randomized subjects. An estimated total of 12 subjects will be included per dose level (in total 6 dose groups). If less than 9 subjects are evaluable per dose level, addition of new a subject to replace a discontinued subject can be allowed.

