3.5 Subject Replacement

Subjects who consented to study participation but discontinued prior to IMP administration (dosing) may be replaced. Subjects withdrawn after dosing may be replaced at the Sponsor's discretion after consultation with the Investigator.

4. Assessments

The overall Schedule of Assessments is given in Appendix Table 1. Details about each visit and the assessments made during the visit are given in the sections in the CSP that are listed in Appendix Table 1.

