5.8 Changes to Planned Analysis

No changes for the main protocol planned analysis have been made. The formal analysis of the pH data and the association between the concentration and pH data was not defined in the protocol but introduced only in the SAP. Also, the PK/PD analysis set is a new analysis dataset defined only in the SAP.

6. References

- 1. Clinical Study Protocol CX842A2107. Final version 4.0 dated 10MAR2023.
- 2. Statistical Principles for Clinical Trials (ICH Topic E 9). EMEA. September 1998, CPMP/ICH/363/96.

7. Appendix

Table 1. Overall schedule of events

Visit → Assessment↓	CSP Section	Visit 1 Screening	Visit 2 Residential	Visit 3 and Visit 4 Outpatient	Visit 5 Residential	Visit 6 Outpatient	Visit 8 Telepho follow-u	
Day→		Day -28 to Day -2	Day -2 to 2	Day 5 and Day 10	Day 14 to Day 15	Day 16	7 days (days) po dose ¹	
Informed consent	11.2.1	X						
Eligibility criteria	9.4, 9.5	X	X ²					
Demographics	11.2.3	X						
Weight/height (BMI)	11.2.4	X						
Medical/surgical history	11.2.5	X						
HIV, Hep B and C test	11.2.7	X						
FSH test ³	11.2.8	X						
Pregnancy test	11.2.9	X	X					
Urine drug screen	11.2.10	X	X ⁴					
Alcohol test	11.2.11	X	X ⁴					
Screening for Helicobacter Pylori	11.4.5	x						
Safety laboratory profile	11.4.3	X	X	Х	Х	X		
Vital signs ⁵	11.4.4	Х	x		Х			

Statistical Analysis Plan

CX842A2107

Version 2.0, 04-Oct-2023

Visit → Assessment↓	CSP Section	Visit 1 Screening	Visit 2 Residential	Visit 3 and Visit 4 Outpatient	Visit 5 Residential	Visit 6 Outpatient		Visit 8 Telephone follow-up
Physical examination	11.4.2	Х	Х		Х			
12-lead safety ECG	9.9	Х	Х		Х			
Randomization	10.5	X ⁶						
IMP administration ⁷	11.3.1		X	X	X			
PK blood sampling ⁸	11.3.2		X	X	Х	X		
Intragastric pH measurement	9.6.1		x		х			
Standardized meals	10.5		X		X			
Hand-out of linaprazan glurate ⁹	10.7		x					
Compliance check	N/A				X			
Overnight stay in clinic	11.2.12		X		X			
Baseline symptoms ¹⁰	11.4	X						
AEs ¹¹	9.6.2			X				
Prior and concomitant medications	11.2.1	X						

BMI: Body mass index. CSP: Clinical study protocol. FSH: follicle stimulating hormone. HIV: Human immunodeficiency virus. IMP: Investigational medicinal product. PK: Pharmacokinetic.

- 1. A final remote follow-up visit (Visit 8) will be conducted via telephone 7 days (±2 days) after the final dose of IMP, or after early withdrawal, to follow-up on AEs and concomitant medications.
- 2. Confirmation of eligibility prior to start of baseline pH-measurement.

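### Gender stratifies the randomisation but is in neither HTR mixed model; if it predicts HTR beyond baseline, the LSM confidence intervals are wider than necessary (minor)

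*SAP*

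**What the plan says.** Section 3.3 of the SAP: "Block randomization (block size=6) stratified by gender will be used to generate the randomization list", with allocation to one of six dose groups. Section 3.4.1 plans 12 subjects in each of the six groups: "116 healthy volunteers are planned to be screened to achieve 72 randomized subjects".

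Section 2.4 makes the percentage of time with gastric pH above 4, on Day 1 and Day 14, a primary endpoint. Section 5.7 specifies the model for it and for the cut-offs 5 and 6: "The model will include the dose group, day (day 1, day 14) and the interaction between the dose group and day as fixed effects", with the matching baseline HTR as covariate and subject as random effect. Its output is an LSM with 95% CI for each dose group and day. For sensitivity, a model "excluding the baseline covariate will also be fitted to support the results from the primary statistical model". Neither model contains gender, and no reason is given.

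Section 5.8 says that the formal pH analysis "was not defined in the protocol but introduced only in the SAP", so section 5.7 is where the model terms are fixed.

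Two passages foresee later losses. Section 3.4.1: "If less than 9 subjects are evaluable per dose level", a replacement may be added. Section 3.5: "Subjects withdrawn after dosing may be replaced at the Sponsor's discretion".

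**The concern.** Stratified blocks balance gender across the dose groups. The LSMs then vary less from gender than they would under simple randomisation. A model without gender does not use this: its residual variance still contains any gender difference that baseline HTR does not explain, so the reported standard errors are too large. The sensitivity model lacks baseline HTR as well and so leaves the whole gender difference in the residual.

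The LSMs with 95% CIs are the only model-based estimates of the primary PD endpoint, and they are plotted by dose group. No between-group test is specified, so the interval is the main inferential result. Precision is what is at stake. A lesser point is that, if exclusions, failed pH recordings, dropouts or replacements leave the groups with different gender mixes, an unadjusted LSM carries that difference. Imbalance at allocation is not the issue: with blocks of six over six groups, any two groups differ by at most one subject of each gender.

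**Working it through.** **The plan's own figure.** 6 groups × 12 = 72 randomised, as section 3.4.1 states. The SAP gives no power, SD, gender effect or target CI width, so no further stated figure can be reproduced.

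**Inputs**
- From the SAP: 72 subjects, six groups of 12, one baseline covariate, 95% CIs.
- Assumed: *d*, the gender difference in HTR on a given day after adjustment for baseline HTR, in units of the within-gender residual SD; and *p*, the share of one gender, equal in all groups. The gender shift is taken as constant over dose groups and days.

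**Width of the intervals.** Between-subject residual degrees of freedom are 72 − 6 − 1 = 65 without gender and 64 with it. Without gender, the residual sum of squares is expected to be 64 + 1 + 72·p(1−p)·d² in units of the within-gender variance. Hence

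CI width ratio (without / with gender) = √[(65 + 72·p(1−p)·d²) / 65] × t(0.975; 65) / t(0.975; 64).

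The ratio of t quantiles is practically 1. At p = 0.5, 72·p(1−p) = 18, so for d = 0.5 the ratio is √[(65 + 18 × 0.25)/65] = √(69.5/65) = 1.034. For d = 1.0 it is √(83/65) = 1.130. Effective group size is 12 / ratio².

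| d (SD) | Ratio, p = 0.5 | 12 subjects act like | Ratio, p = 0.25 |
|---|---|---|---|
| 0 | 1.000 | 12.0 | 1.000 |
| 0.25 | 1.008 | 11.8 | 1.006 |
| 0.5 | 1.034 | 11.2 | 1.025 |
| 0.8 | 1.085 | 10.2 | 1.064 |
| 1.0 | 1.130 | 9.4 | 1.099 |

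**Cross-checks.** A slightly different approximation, √[1 + p(1−p)·d²·12/11] times the same ratio of t quantiles, gives 3.3%, 8.3% and 12.8% excess width at 0.5, 0.8 and 1.0 SD for p = 0.5. A simulation of the two-day model with random subject effect and baseline covariate (3000 runs per setting, within-subject correlation 0.3 to 0.8) gives mean half-width ratios of 1.000, 1.008–1.009, 1.032–1.034, 1.083–1.085 and 1.130 for the five values of d. Simulated coverage is 94.4–97.7% without gender and 94.2–95.7% with it.

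**Imbalance after losses.** Assume each group starts with 6 men and 6 women and loses 3 at random, leaving 9. The number of men lost is 0, 1, 2 or 3 with probability 20/220, 90/220, 90/220 and 20/220. For two such groups the counts differ by 1, 2 or 3 with probability 0.4835, 0.1488 and 0.0165. So:
- mean absolute difference in male share = (0.4835 + 2 × 0.1488 + 3 × 0.0165)/9 = 0.092;
- probability of a difference of at least 2/9 = 0.1488 + 0.0165 = 0.165;
- maximum = 3/9 = 0.333.

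The mean absolute shift in the difference between two LSMs is 0.092 × d: 0.05 SD at d = 0.5 and 0.09 SD at d = 1.0. With 9 per group the standard error of that difference is about √(2/9) = 0.47 SD. The typical shift is therefore about a tenth of a standard error at d = 0.5 and a fifth at d = 1.0.

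**The case against.** The case against runs as follows.

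- **Nothing is contradicted.** The SAP never undertakes to adjust for its stratification factor, and an SAP does not ordinarily justify each covariate it omits. This is true. The point concerns how well the model is chosen, not an inconsistency.
- **The effect is unsupported.** Nothing in the SAP says that gender predicts HTR, still less after adjustment for the subject's own baseline HTR, which may absorb much of any gender difference. This stands, and it is why the result is given as a range starting at zero. The 0.8 and 1.0 SD rows are an upper end that the documents do not support. The argument does not cover the sensitivity model, which has no baseline covariate.
- **No decision turns on the width.** There is no power statement, margin, between-group test or success criterion. This also stands and keeps the point minor.
- **The shift after losses is small and not a second harm.** Under random losses it averages zero and is part of the sampling variation that the unadjusted residual variance already contains. This is right: it should not be added to the precision loss. It matters only for the gender mix actually observed, and would be systematic only if losses differed by gender between dose groups. Nine evaluable per group is also the limit below which replacement is allowed, not the expected case.
- **The calculation is idealised.** HTR is bounded at 100%, and the planned bar-plot categories are fine near the top, so a constant gender shift and common SD may not hold. The gains are therefore approximate.

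None of this gives a reason to leave the factor out. Adding it does little harm even if gender turns out to be irrelevant.

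**Conclusion.** The concern holds, as a minor one. Gender is a stratification factor and is absent from both HTR models, and section 5.8 gives no ground to expect the term from the protocol. The consequence is conditional: with no gender effect beyond baseline HTR, nothing is lost. With half of each gender, a residual difference of 0.25 to 0.5 SD makes the intervals about 0.8% to 3.4% wider than needed, and 0.8 to 1.0 SD makes them 8.5% to 13% wider. With a quarter of one gender the corresponding figures are 0.6% to 2.5% and 6.4% to 9.9%. All of these rest on assumed gender effects and gender splits and on a constant gender shift. Coverage is nominal or conservative, so no planned inference becomes invalid.

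**What to change.** In section 5.7, add gender as a fixed effect to the mixed model for each of the three pH cut-offs and to the sensitivity model without baseline HTR. State that LSMs are computed at the same gender mix for all dose groups, namely the observed overall proportions. Without a gender interaction this choice sets the level of the LSMs and does not affect the differences between them. If gender is left out on purpose, give the reason there in one sentence.

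The cost is one term in the model statement and about one degree of freedom (65 to 64). If gender has no effect, CI width changes by less than 0.1%. Gender is already collected (section 4.2) and is on the randomisation list (section 3.3).

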2.3 Exploratory Objectives

2.4 Primary endpoints

- Linaprazan glurate and linaprazan PK parameters after single and repeated administration of linaprazan glurate (when applicable):
 - $\circ~$ Area under the plasma concentration vs. time curve (AUC) at different timepoints: AUC_{0-24}, AUC_{0-12}, AUC_{12-24}, AUC_{24-48}, and AUC_{0-t}.
 - The minimum, end-of dosing interval, maximum and average plasma concentrations C_{trough}, C_{max}, C_{aver}.

Statistical Analysis Plan CX842A2107 Version 2.0, 04-Oct-2023

- Percentage of time gastric pH >4 at Day 1 and Day 14, over a 24-hour monitoring period following linaprazan glurate administration.

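### Read as written, the section 5.7 HTR model gives Day 1 and Day 14 one common variance, so the per-day 95% CIs would be miscalibrated if the two days differ in spread

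*SAP*

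**What the plan says.** Section 2.4 lists among the primary endpoints "Percentage of time gastric pH >4 at Day 1 and Day 14". Section 5.7 gives the model: "A Mixed Model for Repeated Measurements (MMRM) will be utilized to analyze the percentage of time with intragastric pH >4, pH >5, and pH >6", with one fit per cut-off. On the fixed part it says: "The model will include the dose group, day (day 1, day 14) and the interaction between the dose group and day as fixed effects". That sentence ends with "the corresponding baseline HTR as a covariate and subject as a random effect". It states no within-subject covariance structure, no day-specific variance and no degrees-of-freedom method.

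The stated output is LSMs whose "95% confidence intervals (CI) will be used to estimate the HTR for each dose group and day"; they are also plotted by visit for each dose group. The one alternative model is described as follows: "As a sensitivity analysis a MMRM-model (separately for the three pH cutoffs) excluding the baseline covariate will also be fitted". Section 5.8 says that the formal pH analysis was introduced in the SAP and is not in the protocol, so on the SAP's own account this sentence is where the model is defined.

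**The concern.** A random subject intercept with a single residual variance makes the variance on Day 1 equal to the variance on Day 14. The SAP gives some reason to doubt that equality:

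- Day 1 includes the onset of effect after the first dose. Section 5.7.1 itself leaves the first two hours after that dose out of its scatterplots.
- HTR cannot exceed 100%, and the bar-plot categories in section 5.7 are finest near the top. On a bounded scale the spread usually changes with the mean, and the group-by-day interaction is there because means may change by day.
- Most doses between the two recordings are taken at home (section 5.4.6), so differences in adherence could affect Day 14 but not Day 1.

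None of this fixes the direction or the size of a difference, which is a reason to estimate the two variances rather than set them equal.

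What is at stake is the interval for each dose group on each day. Section 5.7 plans no hypothesis test on HTR, so those intervals carry the inference for the primary PD endpoint.

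**Working it through.** **Inputs from the SAP.** There are six dose groups, and section 3.4.1 says "An estimated total of 12 subjects will be included per dose level (in total 6 dose groups"). Check: 6 × 12 = 72, the planned number randomized. There are two modelled days. The SAP states no HTR standard deviation, interval width or power, so no other figure can be reproduced.

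**Assumed inputs.** The SDs of HTR on each day, given dose group and baseline, in percentage points: 15/15, 15/12, 15/10 and 16/8. All groups are taken to have the same SD on a given day. The between-day correlation ρ is 0.5 in the simulation below.

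**Step 1: what compound symmetry estimates.** Write s1 and s2 for the true SDs on the two days. With complete data, REML works from each subject's mean m and difference d:

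- Var(m) = (s1² + s2² + 2ρ·s1·s2)/4
- Var(d) = s1² + s2² − 2ρ·s1·s2
- Variance assigned to either day = Var(m) + Var(d)/4 = (s1² + s2²)/2

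The correlation cancels. Both days receive the average of the two variances, so s_pooled = √[(s1² + s2²)/2].

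**Step 2: half-width and coverage at n = 12 per group.** The degrees of freedom under the SAP model are roughly 100, so t = 1.984. With a separate variance per day they are 72 − 6 − 1 = 65, so t = 1.997. The small contribution from estimating the baseline slope is left out.

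- Half-width under the SAP model, same on both days: 1.984 × s_pooled/√12
- Half-width with the day's own variance: 1.997 × s_day/√12
- Coverage on a day ≈ 2Φ(1.984 × s_pooled/s_day) − 1

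Worked case, SD 15/10: s_pooled = √[(225 + 100)/2] = 12.75. Half-width = 1.984 × 12.75/3.464 = 7.30. Coverage on the SD 15 day is 2Φ(1.686) − 1 = 90.8%, and on the SD 10 day 2Φ(2.529) − 1 = 98.9%.

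| SDs (larger/smaller) | s_pooled | SAP half-width, both days | Half-width with own variance | Approximate coverage under the SAP model |
|---|---|---|---|---|
| 15/15 | 15.00 | 8.59 | 8.65 / 8.65 | 95.3% / 95.3% |
| 15/12 | 13.58 | 7.78 | 8.65 / 6.92 | 92.8% / 97.5% |
| 15/10 | 12.75 | 7.30 | 8.65 / 5.77 | 90.8% / 98.9% |
| 16/8 | 12.65 | 7.24 | 9.22 / 4.61 | 88.3% / 99.8% |

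If Day 1 has the smaller SD, the two coverages swap: 10 on Day 1 and 15 on Day 14 gives 98.9% and 90.8%.

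**Step 3: simulation of the SAP model against the proposed model.** Six groups of 12, a common baseline slope and ρ = 0.5. The SAP model covered about 92%/97% at 15/12, 91%/99% at 15/10 and 88%/99.8% at 16/8, in line with step 2. The unstructured 2x2 model covered about 95% on both days. At equal SDs its half-width was 8.64 against 8.59, a rise of 0.05/8.59 = 0.6%.

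**Step 4: fewer subjects.** Section 3.4.1 mentions 9 evaluable subjects as the point below which replacement can be allowed. At 9 per group the approximate coverage moves by no more than 0.2 points (20/10: 88.5%/99.8%, against 88.3%/99.8% at 12).

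**Step 5: unequal groups.** With day SDs 20/16 and group SD multipliers running from 1.5 down to 0.4, the most variable group covered 77% on one day and 88% on the other. Its intervals were too narrow on both days, so the pattern of narrow on one day and wide on the other requires similar variance across groups.

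**The case against.** - **MMRM often implies a repeated-measures covariance.** This stands in part. The label leaves room for one, and the SAP does not exclude it. But no such structure is written, and the term that is written is the random subject effect. Two programmers could produce different intervals from this sentence.
- **The size is assumed.** This stands. The SAP gives no SDs, and at a mild ratio (15/12) the effect is modest.
- **A reader might infer that the intervals go wrong in opposite directions in every group whenever the days differ.** The documents do not support that. It needs similar variance across dose groups, and step 5 shows a group that is too narrow on both days.
- **The impact is limited.** This stands in part. It is a Phase I estimation study, section 5.7 attaches no decision rule to these intervals, and descriptive statistics (with SD, under section 5.2.1) are planned by dose group and day. A reader would see the day-specific spread beside the model intervals. That does not correct the intervals.
- **It duplicates any point about variance between dose groups.** It does not. The restriction across days would remain if all six groups were equally variable.

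**Conclusion.** The point holds conditionally. Read as written, the model gives both days one variance, and the baseline-free sensitivity model cannot reveal this because it carries the same restriction. If the days differ in spread and the groups are similarly variable, nominal 95% intervals cover about 92%/97% (SD 15/12) to 88%/99.8% (SD 16/8), with the lower figure on the more variable day. These sizes rest on assumed SDs; which day is the more variable is unknown.

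Two stronger readings should be avoided. The SAP does not show that the Day 1 and Day 14 variances actually differ, so it cannot be said that the planned intervals are wrong. Nor are the estimated HTR values put in doubt: with complete data the LSM point estimates are essentially unaffected, and the problem lies in the per-day intervals.

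This should be changed because those intervals are the model's stated output for a primary endpoint and the better specification is almost free.

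**What to change.** In section 5.7, replace the random-subject clause with: *day as the repeated factor within subject, unstructured 2x2 covariance, REML, Kenward-Roger degrees of freedom, no additional random subject effect*. Apply it to the primary and the sensitivity model at pH >4, >5 and >6. Keep the random-intercept model only as a fallback if the unstructured fit does not converge.

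The cost is one sentence in the SAP, a line of code and one extra variance parameter estimated from the 72 planned subjects. If the SDs are equal after all, the half-width rises by less than 1%. A 2x2 covariance common to all groups does not cure variance that differs between dose groups; that needs its own remedy.
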